5.10 Interim Analyses and Data Monitoring

No interim analysis or assignment of a data monitoring committee is planned.

5.11 Multi-Center Studies

Considering that the number of subjects per center will be low, the center will not be considered as an explicative factor in the statistical analyses.

5.12 Multiple Testing

Due to the proof-of-concept purpose of this trial, no alpha-level adjustment for multiplicity will be applied.

5.13 Dry Run

Blinded dry-run(s) will occur prior to final database lock and unblinding in order to allow a review of clinical trial data and tables, listings, and figures. Consequences on the statistical analysis will be discussed and documented.

6 Summary of Study Data

6.1 Subject Disposition

Patient disposition will be tabulated overall, by treatment group and stratification factor and will include the number of patients who are screened via the social media recruitment path, screened via on-site recruitment path, randomized, completed the study, and discontinued the study during the double-blind period (including reasons).

The number and percentage of patients in each analysis set and reason for exclusion will be summarized overall, by treatment group and stratification factor.

Patient enrollment by study site will be tabulated by treatment group and overall.

A by-patient listing of inclusion into analysis sets and study completion information including reason for study drug discontinuation or early withdrawal from study, if applicable, will be presented.

6.2 Screen Failures

The reason(s) for screen failures will be listed.

6.3 Protocol Deviations

Protocol deviations for lack of compliance, mis-stratification, inadequate or missing informed consent, intake of study treatment other than the one assigned, incorrect doses and prohibited treatments, missed visits, missed assessments, out-of-window visits or assessments, and violations of inclusion/exclusion criteria (where possible) will be determined based on available data. All other protocol deviations will be collected by the clinical research associates.

Protocol deviations that could potentially affect the efficacy or safety conclusions of the study will be identified, and the assessment of determination of evaluable patients for analysis populations (FAS, mFAS, SAF, PP and PK) will be performed and approved by the Study Statistician, Medical Monitor, and Clinical Study Manager prior to database lock and unblinding of individual patient treatment information.

The process applied for the identification of protocol deviations will be described in a specific document.

All protocol deviations will be listed and summarized by treatment group. To identify deviation categories and sub-categories for summarization, the "Sponsor PD Number" variable in the excel workbook containing the list of protocol deviations will be used. The main category will be identified by the first number and the sub-category will be identified by the second number. As an example: if a code is "1.3", "1" is the main category code and "3" is the sub-category code.

6.4 Demographic and Baseline Variables

Subject demographics and other baseline characteristics measured before randomization will be summarized descriptively by treatment group on the FAS and, if the PP set comprises less than 80% of the FAS, also on the PP set. Summaries will be provided by treatment group as well as overall. Summaries by L-BT status at screening will also be presented. A by-patient listing will also be provided.

Demographic variables will include the following:

- 1. Age at inform consent
- 2. Class age (≥18 and <30; ≥30 and <50; ≥50 and <65; ≥65) at informed consent

- 3. Sex
- 4. Race
- 5. Ethnicity

Other baseline characteristics will include the following:

- 1. Weight (kg)
- 2. Height (cm)
- 3. Body mass index (BMI) (kg/m²)
- 4. Childbearing potential (for females only)
- 5. Alcohol consumption
- 6. Smoking habits
- 7. Drug abuse

Additionally, baseline disease characteristics and medical history questionnaire responses will be summarized descriptively and provided in a by-patient listing.

6.5 Medical History

Verbatim terms on eCRFs will be mapped to preferred terms (PTs) and system organ classes (SOCs) using Medical Dictionary for Regulatory Activities terminology (MedDRA).

Medical history will be summarized by SOC, PT, and treatment group (and overall) for the SAF. Summaries will be ordered by descending order (based on total) of incidence of SOC and PT within each SOC. A by-patient listing will also be provided. Conditions will be classified as 'previous' or 'ongoing' at baseline.

Summaries will be done for:

- Previous medical and surgical history not related to rosacea
- Ongoing medical and surgical history not related to rosacea

6.6 Concomitant Medications

Medications will be considered as prior if they stopped before the first study drug intake.

Prior and concomitant medications will be coded using the World Health Organization Drug Dictionary (WHO-DD) and will be classified according to the default Anatomical Therapeutic Chemical (ATC) classification system code (up to 4 levels), WHO-DD Drug Name, and Preferred Term (PT).

Prior and concomitant medications will be summarized separately for the SAF by the ATC Class Level 1 category, Level 2 category and PT. Subjects may have more than one medication per ATC category and PT. At each level of subject summarization, a subject will be counted once if he/she reports one or more medications at that specific level. The prior medication frequency distribution table will be displayed by the safety treatment arms and all subjects even though the prior medication information was collected prior to dispensing study drug.

Additionally, prohibited concomitant medications will also be summarized.

Prohibited concomitant medications from V1 to V4 include:

- Initiation of beta-blocker treatment (ATC = C07)
- Initiation of any oestroprogestinic or progestogen contraceptive or oestroprogestinic or progestogen replacement therapy (ATC = G03 [excluding G03XB], G02B)

- Biologic or non-biologic immunomodulatory or immunosuppressive drugs (ATC = L); warfarin (or other coumarins) (ATC = B01AA); niacin (ATC=A11HA); topical facial or systemic antibiotic treatments (ATC = J01, D01, D06); neomycin or any other low-absorbable oral antibiotics (such as marketed rifaximin) (ATC = A01AB, B05CA, J01GB, R02AB, A07A); topical facial, inhaled or systemic corticosteroids (ATC = D07, H02, A01AC, A07EA, D10AA, M01BA, N02CB, R01AB, R01AD, R03AK, R03AL, R03BA); topical and systemic retinoids (ATC = D05BB, D10AD, D10BA, L01XF); any other topical or systemic treatment for rosacea (including also laser and pulsed light, etc.) (ATC = D).
- Any cancer-related treatment (ATC = L).
- "Over the counter" formulations including intestinal and topical skin probiotics (ATC=A07F).
- Any other experimental treatment.

6.7 Study Drug Accountability

Subjects will be dispensed blinded study drug according to the randomization schedule the Day 1 visit. Subjects will receive the study drug tablets in two bottles: a White bottle and a Yellow bottle. Possible tablet strengths are 0 mg and 250 mg. Subjects will be instructed to take 1 tablet of investigational product from each bottle three times daily by mouth, in order to maintain study blinding.

The following data will be collected and derived at the end of the Day 30 visit interval:

Parameter	Origin/Derivation		
Tablets Dispensed Amount	CRF		
Tablets Returned Amount	CRF		
Expected Number of Tablets Taken	Derived: ((Date of Last Dose – Date of First Dose) x 6) + 2)		
Estimated Number of Tablets Taken	Derived: Number of Tablets Dispensed Amount – Number of Tablets Returned Amount		
Treatment Compliance (%)	Derived: 100 x Estimated Number of Tablets Taken / Expected Number of Tablets Taken (approximated to one number after the decimal point)		

The Overall Treatment Compliance (%) will be calculated as:

100 x (Estimated Number of Tablets Taken) / (Expected Number of Tablets Taken), and approximated to one number after the decimal point.

The computed treatment compliance will be listed and summarized descriptively. Compliance input into the eCRF will not be listed or summarized.

The following compliance categorical ranges will be defined:

<=80%, 80-100%, >100%, and Not Reported

All study drug accountability comments will be provided in a subject listing. Descriptive statistics of percent compliance, as continuous and categorical variable (<=80, 80-100, >100) will be presented by treatment group and stratification factor on the FAS and PP.

6.8 Study Drug Exposure

The study drug will be packaged in a way that each TID dose will be split between two separate colored bottles (White and Yellow), with the following blinded configuration for each treatment arm:

- 250 mg Rifaximin-EIR TID dose: one bottle of tablets will be placebo and one bottle of tablets will be 250 mg strength
- 500 mg Rifaximin-EIR TID dose: Both bottles of tablets will be 250 mg strength
- Placebo dose: Both bottles of tablets will be placebo

Due to the nature of this study and data collection, it will be assumed each tablet taken by the subjects will have equal treatment weight for study drug compliance and exposure. After database lock and when the study drug treatment is unblinded, each bottle number assigned to a subject will be checked to verify that correct treatment arm was given based on the randomization schedule. Any incorrect treatment given where the estimated number of tablets taken defined in Section 6.7 is greater than zero, will be defined as a major protocol deviation. Study drug exposure will be listed and summarized based on the treatment arm subjects received.

The number of study days of study drug exposure (overall treatment duration) will be calculated as the date of last dose minus the date of first dose + 1 and will be summarized on the SAF using descriptive statistics. The date of first dose will be collected in the Study Drug Administration Form. If the last dose date of study drug was not collected in the Study Drug Compliance eCRF page it will remain missing.

7 Efficacy Analyses

7.1 General Considerations

The primary statistical analysis on the FAS will be performed according to the actual treatment received.

In addition, two sensitivity analyses will be implemented for the primary analysis:

- The first by analyzing the FAS according to the "randomized treatment", as originally planned
- The second on the mFAS according to the "randomized treatment"

Selected analyses of the efficacy endpoints will also be performed on the PP set as supportive analyses. For details as to which populations will be used for each analysis please refer to the TLF Shells document.

For the efficacy endpoints which use Analysis of Covariance (ANCOVA) models, least squares (LS) means will be used to compare each active treatment arm with placebo. The active treatment arms will not be themselves compared. The LS mean differences will be presented with 95% CIs and p-values.

The binary efficacy endpoints expressed as percentages will be analyzed by means of a two-sided Cochran Mantel-Haenszel Chi-square test stratified by L-BT status at Screening. The Breslow-Day test for stratified tables will be applied. A two-sided 95% CI for difference of success rate between each active treatment arm vs placebo will also be computed.

For efficacy endpoints addressing results at both end of treatment (V3) and end of study (V4), analysis for each visit will be conducted separately.

7.2 Primary Efficacy Analyses

The co-primary efficacy endpoints, clinically assessed by the Investigator, are the change from baseline in total number of rosacea inflammatory lesions (papules and pustules) at the end of treatment, and the percent of subjects showing treatment success, defined as an IGA score of 0 (clear) or 1 (almost clear) with at least a 2-grade improvement from baseline at the end of treatment.

The first co-primary efficacy endpoint (change from baseline in number of inflammatory lesions at end of treatment (Day 30)) will be analyzed by means of an Analysis of Covariance (ANCOVA) model (one model for each comparison to placebo), with change from Baseline to Day 30 as dependent variable, treatment group and L-BT status at screening as explicative factors, and baseline number of inflammatory lesions as covariate.

The adjusted mean differences with the corresponding 95% confidence interval will be estimated from the model. The 95% confidence interval for the difference between adjusted mean differences of each active treatment arm versus the placebo arm will be also presented.

The second co-primary efficacy endpoint (percent of patients showing treatment success) will be analyzed by means of a stratified (by L-BT status) Cochran Mantel-Haenszel (CMH) chi square test. The Breslow- Day test with Tarone's adjustment for stratified tables will be applied. A two-sided 95% CI for difference in success rate between the treatment groups (each active group vs placebo) overall and by L-BT status will also be computed.

For each co-primary endpoint, inferential statistical analyses will be completed for each subgroup described in Section 5.7.

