9.2 Inclusion Criteria

All the following criteria must be met both at the Screening and Randomization visits unless otherwise specified.

- 1. Men and women aged 18 years or older at screening (V1)
- 2. Female participants are eligible if they are:

of non-childbearing potential, i.e.: i) post-menopausal (at least 2 years without spontaneous menses), or ii) surgically sterile (bilateral tubal occlusion, or hysterectomy), or iii) ablation of both ovaries),

or

of childbearing potential with a negative pregnancy test result at screening and randomization and agreeing to use a highly effective method of contraception (i.e. with failure rate of less than 1% per year) until 72 hours after taking the last study treatment dose.

Note 1. Based on Clinical Trial Facilitation Group recommendations, highly effective methods of contraception are the following:

- intrauterine device (IUD);
- intrauterine hormone-releasing systems (IUS) or;
- combined hormonal contraceptives (i.e. estrogen and progestogen) in oral, intravaginal or transdermal form, with inhibition of ovulation as primary mode of action or;
- progestogen-only hormonal contraceptives in oral, injectable or implantable form, with inhibition of ovulation as primary mode of action or;
- absolute and continuous sexual abstinence from Day 1 included (first day of treatment) until 72 hours after taking the last study treatment dose.

Note 2. In each case of delayed menstrual period (over one month between menstruations), female participants of child-bearing potential will be strongly recommended a confirmation of absence of pregnancy. This recommendation applies also to women of child-bearing potential with infrequent or irregular menstrual cycles.
- 3. Presence of rosacea, papulopustular phenotype, defined as papules and/or nodules, with or without pustules of rosacea, without comedones, plus: centrofacial persistent erythema or phyma or transient episodic facial erythema (flushing) or facial telangiectasia (excluding perialar regions) or major ocular rosacea features (i.e. lid margin telangiectasia, interpalpebral conjunctival injection, spade-shaped infiltrates in the cornea, scleritis and sclerokeratitis).
- 4. Presence of \geq 11 and \leq 70 facial papules and/or pustules.
- 5. Moderate (Grade 3) or severe (Grade 4) rosacea based on Investigator's Global Assessment (IGA) based on Investigator's judgement.

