10.3 Method of Assigning Subjects to Treatment Groups / Randomisation

A unique subject's identification number will be assigned to all subjects consenting to be enrolled in the study obtained concatenating the center number with the screening number.

A subject who fails to meet the protocol eligibility criteria will be identified as screening failure; his/her identification number will not be reallocated.

Randomisation will occur at visit V2 after all baseline procedures have been performed and eligibility for the study has been confirmed.

Participants will be randomised, on a 1:1:1 basis, to Rifaximin-EIR 250 mg three times a day (750 mg daily) for 29 consecutive days and Rifaximin-EIR 250 mg single dose on Day 30, Rifaximin-EIR 500 mg three times a day (1500 mg daily) for 29 consecutive days and Rifaximin-EIR 500 mg single dose on Day 30, or placebo for 30 consecutive days.

Blocks will be used to assure treatment balance.

Patients will be stratified at randomization based on their L-BT status (negative vs. positive) and PK sub-study participation (yes or not).

Randomization will occur throughout an IWR system integrated into the e-CRF.

At V2, the randomization system will assign an individual Patient's kit number based on a pre-defined randomisation list.

The enrolment will be competitive.

Decoding of randomization in case of emergency is described in chapter 11.4.

The subjects will be offered participation to the PK sub-study. If they agree, they will be randomized according to the relevant stratum maintaining treatment balance among groups; otherwise, they will enter the main study.

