4.3 Subject Randomization

Randomization will be carried out using an interactive response technology (IRT) system, with central randomization following a 1:1:1 ratio between the 3 treatment arms, based on a block randomization method. Randomization will be stratified by the following factor:

- L-BT status H₂ ≤ 10 ppm
- L-BT status H₂ > 10 ppm

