5.4.4 Full Analysis Set

The primary efficacy analysis population will be the Full Analysis Set (FAS), defined as all randomized patients having taken at least one dose of the investigational treatment and have at least one post baseline assessment for any of the two co-primary endpoints.

To mitigate the impact of the treatment kit misallocations, the primary statistical analysis on the FAS will be performed according to the actual treatment received (not according to the "randomized" treatment, as per ITT principle).

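### The IGA-success co-primary is tested without baseline IGA grade, although grade 4 patients must improve further; adding it would give a modest gain in precision and robustness at little cost

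*SAP*

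**What the plan says.** Protocol 9.2 admits patients with "Moderate (Grade 3) or severe (Grade 4) rosacea based on Investigator's Global Assessment (IGA) based on Investigator's judgement". SAP 7.2 counts a success as a patient "defined as an IGA score of 0 (clear) or 1 (almost clear) with at least a 2-grade improvement from baseline at the end of treatment", and says that this endpoint "will be analyzed by means of a stratified (by L-BT status) Cochran Mantel-Haenszel (CMH) chi square test". SAP 7.1 gives the same single stratifier for all binary efficacy endpoints. Protocol 16.3.1 calls the test stratified without naming the factor.

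Baseline IGA appears nowhere else in the inferential plan:
- It is not a randomisation stratum. Protocol 10.3 names L-BT status and PK sub-study participation; SAP 4.3 names L-BT status only.
- It is not among the subgroups for the co-primaries (SAP 5.7.1: L-BT status, breath H2, breath CH4).
- It is not part of either sensitivity analysis (SAP 7.1).

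The continuous endpoints are treated differently. The lesion-count co-primary is fitted with treatment, L-BT status "and baseline number of inflammatory lesions as covariate", and each secondary ANCOVA in SAP 7.3 adjusts for its own baseline value. IGA is scored at both V1 and V2 (Protocol 11.1), so the baseline grade is already collected.

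**The concern.** The endpoint sets grade 4 patients a higher hurdle than grade 3 patients. Baseline grade is therefore a likely predictor of success, and it is the natural counterpart of the baseline lesion count that the other co-primary adjusts for. If grade does predict success, leaving it out has two consequences. The test gives up some power. And if one arm happens to receive more grade 4 patients, nothing in the planned test or the confidence interval for the rate difference corrects for it.

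SAP 3.2.1 declares success for a dose only if both co-primaries are met, so the binary comparison bears directly on the study's conclusion.

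**Working it through.** **1. The plan's own figure.** Protocol 16.1 starts from 51 per arm and allows about 10% dropout: 51 / 0.90 = 56.7, rounded up to 57; 57 x 3 = 171, as stated. The final size is 67 x 3 = 201. The 51 itself cannot be rebuilt, because the success rates, lesion difference, SD and power are redacted. All power figures below are therefore assumptions shown over a range.

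**2. The hurdle.** Reaching IGA 1 takes 3 - 1 = 2 grades from grade 3, and 4 - 1 = 3 grades from grade 4. For any eligible entrant, a score of 0 or 1 already implies the 2-grade improvement, so that clause does not even out the hurdle.

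**3. Chance imbalance.** With grade 4 share q, the SD of the between-arm difference in that share at 67 per arm is sqrt(2q(1-q)/67).
- q = 0.15: sqrt(0.255/67) = 6.2 points.
- q = 0.35: sqrt(0.455/67) = 8.2 points.

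If success differs by 15 to 25 points between grades (assumed), one SD shifts the unadjusted rate difference by 0.062 x 15 = 0.9 to 0.082 x 25 = 2.1 points.

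**4. Power, treatment odds ratio 2.8.** Simulated trials with 67 per arm and 40,000 trials per row; CMH by L-BT against CMH by L-BT x baseline IGA, two-sided 5%:

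| Grade 4 share | Placebo success, grade 3 / grade 4 | Grade odds ratio | L-BT only | L-BT x IGA |
|---|---|---|---|---|
| 30% | 20% / 11% | 2.0 | 71.5% | 71.6% |
| 15% | 20% / 5% | 4.8 | 71.3% | 72.2% |
| 25% | 20% / 5% | 4.8 | 67.5% | 68.9% |
| 35% | 25% / 5% | 6.3 | 65.5% | 69.1% |
| 35% | 30% / 5% | 8.1 | 66.5% | 71.3% |

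The grade odds ratio is, for example, (0.20/0.80) / (0.05/0.95) = 4.8. Over 51 to 67 per arm and 10% to 35% grade 4, the change is about -0.7 points when grade is not prognostic, about 0 near an odds ratio of 2, and about +0.5 to +5 points at odds ratios of about 5 to 8.

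**5. A second set of assumptions.** Here the success rates were chosen so that 51 per arm gives about 80% power: placebo 10%, 20% or 30% against active 32.5%, 46% or 57.5%, with 10% to 30% grade 4. Change in power, in points:

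| Grade odds ratio | 51 per arm | 60 per arm |
|---|---|---|
| 1 | -2.5 to -0.4 | -1.1 to -0.3 |
| 2 | -2.2 to +0.4 | -0.6 to +0.5 |
| 4 | -1.1 to +1.9 | 0 to +1.7 |
| 8 | about 0 to +4.0 | +0.6 to +3.9 |

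The losses beyond about 1 point occur at 51 per arm with 30% placebo success. A re-run shows that they largely reflect the discreteness of the two-stratum test at exactly that size; at 60 per arm they have roughly halved.

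**6. Error rate.** Two-sided type I error is about 5% for both tests (4.5% to 5.4% across the second set). It differs once the imbalance is known. In trials where placebo has an excess of grade 4 patients above 1 SD (about one in six per comparison), the one-sided error of the L-BT-only test in favour of the active arm is about 3% to 6% if grade is prognostic. With IGA strata it stays at about 2% to 3%.

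**7. Sparse strata.** With 33 L-BT-negative patients per arm (the cap) and 15% grade 4, that cell holds 33 x 0.15 = about 5 per arm. At 5% success on placebo and 12.8% on active (odds ratio 2.8), the chance of no success in the cell is 0.95^5 x 0.872^5 = about 39%.

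**The case against.** The case for leaving the plan alone is respectable. This is a phase IIa proof of concept with declared exploratory inference and no multiplicity adjustment. Stratifying a CMH by L-BT status, a randomisation factor, is standard. The unadjusted test holds its level, and chance imbalance is already reflected in that level and in the interval's width. Baseline disease characteristics will be summarised (SAP 6.4), so an imbalance would be seen. The documents give no grade 4 share and no success rate by grade. Four strata can cost a little power, leave nearly empty cells, and make a Breslow-Day test over all four uninformative.

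Most of this stands, and it limits the point to precision and robustness. It does not remove the point: seeing an imbalance is not the same as having a prespecified way to account for it, and the likely loss is smaller than the likely gain if grade is moderately or strongly prognostic.

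A reader might infer three stronger things, none of which the documents support:
- **That power is certainly lost.** The loss depends on how prognostic grade is, which is not given, and the sign can reverse.
- **That the binary endpoint sets the study's power.** The inputs for both co-primaries are redacted, so which one drove the 51 per arm is unknown.
- **That adjusting for IGA deals with the kit misallocation.** SAP 5.4.4 says that "the primary statistical analysis on the FAS will be performed according to the actual treatment received", and 15 of the first 30 patients were misallocated. Adjusting for one covariate does not restore randomisation, and nothing links the kit error to severity. The two planned analyses by randomised treatment address that issue.

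**Conclusion.** The gap is real and minor to moderate. The IGA co-primary ignores a baseline value that its own definition makes likely to matter, while the lesion-count co-primary adjusts for its baseline. The planned test is not invalid or biased on average.

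The power gain from adjusting reaches about 5 points only when grade is strongly prognostic and the grade 4 share is about a third. It is near zero when grade is weakly prognostic. If grade is not prognostic the cost is about 1 point near the planned size, or up to 2.5 points at exactly 51 per arm with 30% placebo success. The steadier benefit is protection of the one trial actually run against a chance imbalance in severity. All of these sizes rest on assumed success rates, grade 4 shares and treatment effects; only the structure of the test and the two hurdles come from the documents.

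**What to change.** Before unblinding, amend SAP 7.2 for the second co-primary:
- Stratify the CMH by L-BT status x baseline IGA grade (3 or 4), taking the V2 value under the baseline definition in SAP 5.5.
- Prespecify a rule for sparse strata, based on pooled blinded patient counts and not on outcomes by arm. One option is to merge the two L-BT levels within grade 4 if either falls below a minimum that the SAP names. The blinded dry run (SAP 5.13) can show the pooled grade 4 share.
- Report the Mantel-Haenszel risk difference with its 95% CI over the same strata. The SAP text names no method for this interval.
- Keep the Breslow-Day test with Tarone's adjustment on the L-BT strata alone, so that it does not mix L-BT with severity.
- Keep the CMH by L-BT only as a sensitivity analysis.

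If the sponsor prefers not to change the primary test, the least to do is to prespecify the IGA-stratified version as supportive.

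The cost is SAP wording and a few lines of code, with no new data. The downsides are the small possible loss of power given above and some small strata, which Mantel-Haenszel weighting tolerates.
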